6. RATIONALE AND BACKGROUND

Jardiance (empagliflozin), a highly potent and selective inhibitor of the sodium glucose co-transporter 2 (SGLT-2), was approved in Europe in May 2014 for the treatment of type 2 diabetes (T2D) to improve glycaemic control in adults. Synjardy (empagliflozin/metformin hydrochloride) was approved in Europe in May 2015. SGLT-2 is highly expressed in the kidney; as the predominant glucose transporter, it is responsible for the reabsorption of glucose from the glomerular filtrate back into the circulation. Empagliflozin improves glycaemic control in patients with T2D by reducing renal glucose reabsorption [R14-4617].

The recommended starting dose is 10 mg empagliflozin once daily. In patients tolerating empagliflozin 10 mg once daily who have an estimated glomerular filtration rate (eGFR) \geq 60 mL/min/1.73 m² and need tighter glycaemic control, the dose can be increased to 25 mg once daily. The maximum daily dose is 25 mg [R14-4617].

In Europe, empagliflozin/metformin hydrochloride is available in the following fixed-dose combinations:

- 5 mg empagliflozin plus 850 mg or 1000 mg metformin hydrochloride
- 12.5 mg empagliflozin plus 850 mg or 1000 mg metformin hydrochloride

The recommended dose for the fixed-dose combinations is one tablet twice a day [R17-0153]. Currently, little information is available on whether there is a potential increased risk of cancers of the urinary tract associated with empagliflozin use. Clinical data with empagliflozin has not identified or established a potential mechanism for the development of malignancies. However, “urinary tract malignancies” are listed in the Risk Management Plan (RMP) as a potential risk. The inclusion of renal cancer as a potential risk was based on preclinical toxicology findings and clinical cases of bladder cancer observed with other SGLT-2 inhibitors.

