6.4 RISK OF BLADDER CANCER IN PREVIOUS TRIALS OF SGLT-2 INHIBITORS

In a clinical trial comparing empagliflozin with placebo, three (0.1%) and nine (0.4%) cases of bladder cancer were observed in persons exposed to 10 mg and 25 mg empagliflozin, respectively, while five cases (0.2%) were observed among those with exposure to placebo [P19-01957]. Further, dapagliflozin and canagliflozin, in comparison to placebo, did not increase the risk of bladder cancer in clinical trials [R19-2814, P19-07186]. The hazard ratios (HRs) for dapagliflozin, and canagliflozin were 0.57 (95% CI 0.35-0.93) and 0.90 (95% CI 0.47-1.72), respectively. Therefore, contrary to the preclinical toxicology findings, SGLT-2 inhibitors did not show an increased risk of bladder cancer in clinical trials.

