6.6.2. Assessment of covariate balance before and after matching

The covariates balance between treatment groups before and after matching will be evaluated using:

- Standardized differences (percentage).
- χ^2 test for equality of proportions in dichotomous variables (p-value).
- t-test for equality of means in continuous variables (p-value).

For continuous variables, the standardized difference is defined as

$$d = \frac{(\bar{x}_{\text{empagliflozin}} - \bar{x}_{\text{DPP-4 inhibitor}})}{\sqrt{\frac{s_{\text{empagliflozin}}^2 + s_{\text{DPP-4 inhibitor}}^2}{2}}} \times 100$$

Where $\bar{x}_{\text{empagliflozin}}$ and $\bar{x}_{\text{DPP-4 inhibitor}}$ denote the sample mean of the covariate in empagliflozin users at index date and comparison drug users at index date, respectively, while $s_{\text{empagliflozin}}^2$ and $s_{\text{DPP-4 inhibitor}}^2$ denote the sample variance of the covariate in empagliflozin users at index date and comparison drug users at index date, respectively.

For dichotomous variables, the standardized difference is defined as

$$d = \frac{(\hat{p}_{\text{empagliflozin}} - \hat{p}_{\text{DPP-4 inhibitor}})}{\sqrt{\frac{\hat{p}_{\text{empagliflozin}}(1 - \hat{p}_{\text{empagliflozin}}) + \hat{p}_{\text{DPP-4 inhibitor}}(1 - \hat{p}_{\text{DPP-4 inhibitor}})}{2}}} \times 100$$

Proprietary confidential information © 2024 Boehringer Ingelheim International GmbH or one or more of its affiliated companies

Where $\hat{p}_{empagliflozin}$ and $\hat{p}_{DPP-4\ inhibitor}$ denote the prevalence of the dichotomous variable in empagliflozin users at index date and DPP-4 inhibitor users at index date, respectively [7]

If a categorical variable is defined with more than two categories (i.e. not dichotomous), each category will be treated as a dichotomous variable when computing the standardized differences.

The balance assessment will be performed with regard to the following covariates:

- Demographics and other baseline characteristics at index date Table 11.
- Diabetic complications Table 12 (status at index date).
- Non-diabetic concomitant disease Table 13 (status at index date).
- Diabetic concomitant medication use Table 14 (status at index date).
- Non-diabetic concomitant medication use Table 15 (status at index date).

Balance in baseline characteristics before and after matching between empagliflozin users at index and the DPP-4 inhibitor users at index will be reported in each country, separately.

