All continuous variables will be described using standard statistical measures, i.e. range, mean, standard deviation, median, first and third quartile. All categorical variables will be summarized with absolute and relative frequencies. The standardized differences and p-values for the statistical tests will be also reported.

Results will be reported in 4 tables similar to Table 18.

Standardized difference < 10% will be used as indicator of satisfactory distribution balance after matching [8]. Variables with standardized difference larger than 10% might still exist. The unbalanced variables will be considered as potential confounders and included in the adjustment of Cox's PH model, as described in the comparative analysis (Section 6.7.2). In case a substantial amount of variables remain unbalanced, the PS matching procedure will be re-evaluated by, for example, reducing the caliper width.

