6.7.2. Comparative analysis

Hazard ratios (HRs) for the outcomes defined in Table 8 will be estimated for PS matched cohorts using Cox's PH model with time-varying covariates, if model pre-requisites are fulfilled. HRs will be presented along with 95% CIs. Proportional hazards assumptions for time-fixed exposure variables will be assessed for each model by plotting scaled Schoenfeld residuals.

The comparative analyses will be performed separately for the matched full cohort and matched metformin-user cohort.

Crude model

Crude HRs are calculated using a Cox PH model with as-treated exposure (as defined in Section 5.1.7) as the only included variable.

HRs estimated using the crude model will be presented along with 95% CIs. A table template for the result is given in Table 23. Analysis will be performed separately for each country.

Crude HRs with 95% CIs will be collected from all study countries to carry out meta-analyses as described in Section 6.7.3.2. Results will be reported as in Figure 8.

Base model

Based on the crude model, the base model will be further adjusted with the unbalanced covariates at index date (standard difference $\geq 10\%$) among the variables included in the propensity score model (Section 6.6). The inclusion of adjusting variables will be considered based on data availability as described in Section 10.

HRs estimated using the base model will be presented along with 95% CIs. A table template for the result is given in Table 24. Analysis will be performed separately for each country. HRs with 95% CIs estimated using base model will be collected from all study countries to carry out meta-analyses as described in Section 6.7.3.2. Results will be reported as in Figure 8.

Adjusted model

The base model will be further adjusted with selected time-dependent variables. The following time-dependent variables will be initially considered for inclusion (as detailed in Section 9) in the adjusted Cox's PH model:

- HbA1c value (as defined in Table 11)
- Kidney or genitourinary stones (as defined in Table 13)
- UTI or pyelonephritis (as defined in Table 13)
- Ever exposed to insulin (as defined in Table 14)
- Ever exposed to metformin (as defined in Table 14)

Proprietary confidential information © 2024 Boehringer Ingelheim International GmbH or one or more of its affiliated companies

- Ever exposed to other glucose lowering medication (as defined in Table 14)
- Ever exposed to GLP-1 drugs (as defined in Table 14)

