Hazard ratio estimates using adjusted model	
Using matched cohorts
 
Stratified by gender.
 
(18 tables, 3 outcomes x 2 strata by gender x 3 countries)
	As treated exposure definition	Main outcomes- Table 8	Table 25
Hazard ratio estimates using adjusted model	
Using matched cohorts
 
Stratified by insulin use at index.
 
(18 tables, 3 outcomes x 2 strata by insulin use at index x 3 countries)
	As treated exposure definition	Main outcomes- Table 8	Table 25
Meta-analyses for adjusted HR estimates	
Using adjusted HR estimates and 95% CIs from all study countries.
 
For each stratification variable listed above.
 
(54 figures, 3 outcomes x (3+4+7+2+2) strata)
	As treated exposure definition	Main outcomes- Table 8	Figure 8
Secondary objectives:				
Descriptive analysis				

Analysis	Details	Exposure definition	Outcomes	Template
Stratified incidence rates	Using matched cohorts Country specific analysis (9 tables, 3 outcomes x 3 countries)	Cumulative exposure dose of empaglifloz in	Main outcomes- Table 8	Table 30
Stratified incidence rates	Using empagliflozin users subgroup Country specific analysis (9 tables, 3 outcomes x 3 countries)	Empaglifloz in daily dose	Main outcomes- Table 8	Table 31
Stratified incidence rates	Using empagliflozin users subgroup Country specific analysis (9 tables, 3 outcomes x 3 countries)	Cumulative exposure duration to empaglifloz in	Main outcomes- Table 8	Table 32
Meta-analysis of incidence rates	Using pooled number of outcome events and person-time from all study countries (9 tables, 3 outcomes x 3 secondary exposure definitions)	The secondary exposure definitions listed above	Main outcomes- Table 8	Table 30- Table 32
Secondary objectives: Comparative analysis				
Hazard ratio estimates using adjusted model	Using matched cohorts Country specific analysis (9 tables, 3 outcomes x 3 countries)	Cumulative exposure dose of empaglifloz in	Main outcomes- Table 8	Table 26
Hazard ratio estimates using adjusted model	Using matched cohorts Country specific analysis (9 tables, 3 outcomes x 3 countries)	Empaglifloz in daily dose	Main outcomes- Table 8	Table 27

Analysis	Details	Exposure definition	Outcomes	Template
Hazard ratio estimates using adjusted model	Using matched cohorts Country specific analysis (9 tables, 3 outcomes x 3 countries)	Cumulative exposure duration to empagliflozin	Main outcomes- Table 8	Table 28

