Empagliflozin	x.XXX	x.XXX	x.XXX	x.XXX

Proprietary confidential information © 2024 Boehringer Ingelheim International GmbH or one or more of its affiliated companies

Table 24 Adjusted hazard ratios for [Outcome Name] incidence estimated using the Cox proportional hazards model in the [Study country] matched cohort. The table shows the hazard ratios (HRs) using the base model with the corresponding 95% CI and p-value—As treated exposure definition.

Variables	Hazard ratio	Lower 95% CI	Upper 95% CI	P-value
AT exposure				
DPP-4 inhibitors	reference	reference	reference	reference
Empagliflozin	x.XXX	x.XXX	x.XXX	x.XXX

Proprietary confidential information © 2024 Boehringer Ingelheim International GmbH or one or more of its affiliated companies

Table 25 Adjusted hazard ratios for [Outcome Name] incidence estimated using the Cox proportional hazards model in the [Study country] matched cohort. The table shows the hazard ratios (HRs) using the adjusted model with the corresponding 95% CI and p-value—As treated exposure definition. [Stratifying variable if any]

Variables	Hazard ratio	Lower 95% CI	Upper 95% CI	P-value
AT exposure				
DPP-4 inhibitors	reference	reference	reference	reference
Empagliflozin	x.xxx	x.xxx	x.xxx	x.xxx

Proprietary confidential information © 2024 Boehringer Ingelheim International GmbH or one or more of its affiliated companies

Table 26 Adjusted hazard ratios for [Outcome Name] incidence estimated using the Cox proportional hazards model in the [Study country] matched cohort. The table shows the hazard ratios (HRs) using the adjusted model with the corresponding 95% CI and p-value—Cumulative dose of empagliflozin exposure definition.

Variables	Hazard ratio	Lower 95% CI	Upper 95% CI	P-value
Cumulative dose of empagliflozin				
Never exposed	reference	reference	reference	reference
< Q1	x.xxx	x.xxx	x.xxx	x.xxx
Q1 – Q2	x.xxx	x.xxx	x.xxx	x.xxx
Q2 – Q3	x.xxx	x.xxx	x.xxx	x.xxx
≥ Q3	x.xxx	x.xxx	x.xxx	x.xxx

Proprietary confidential information © 2024 Boehringer Ingelheim International GmbH or one or more of its affiliated companies

Table 27 Adjusted hazard ratios for [Outcome Name] incidence estimated using the Cox proportional hazards model in the [Study country] matched cohort. The table shows the hazard ratios (HRs) using the adjusted model with the corresponding 95% CI and p-value—daily dose of empagliflozin exposure definition.

Variables	Hazard ratio	Lower 95% CI	Upper 95% CI	P-value
Daily dose of empagliflozin				

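### Baseline adjustment in the empagliflozin dose and duration models is chosen on drug-versus-drug balance, so eGFR and other baseline factors that may differ between dose levels can be left out

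*SAP*

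**What the plan says.** SAP 6.10 (Table 16) assigns the comparative analyses for all three secondary exposure definitions to one model in the matched cohorts: "Hazard ratio estimates using adjusted model". The Annex III templates follow this. The one for "daily dose of empagliflozin exposure definition" compares 10 mg and 25 mg with a never-exposed reference group.

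SAP 6.7.2 builds the model in two steps.

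- **Base model.** "Based on the crude model, the base model will be further adjusted with the unbalanced covariates at index date", meaning those with a standardised difference of 10% or more. SAP 6.6.2 sets the contrast on which balance is judged: "Balance in baseline characteristics before and after matching between empagliflozin users at index and the DPP-4 inhibitor users at index will be reported". It also sets the threshold: "Standardized difference < 10% will be used as indicator of satisfactory distribution balance after matching".
- **Adjusted model.** "The base model will be further adjusted with selected time-dependent variables". The nine candidates are HbA1c, kidney or genitourinary stones, urinary tract infection, and ever-use of insulin, metformin, other glucose-lowering drugs, GLP-1 drugs, thiazolidinediones and sulfonylureas. The list does not contain eGFR, age, sex or smoking.

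Protocol Table 4, footnote 4, applies the same imbalance rule to model adjustment.

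If a model fails to converge, SAP 6.7.2 removes covariates one at a time, starting with the smallest standardised difference.

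On dose, Protocol section 6 says that patients who tolerate 10 mg, have an eGFR of at least 60 and "need tighter glycaemic control, the dose can be increased to 25 mg once daily".

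**The concern.** Propensity-score matching makes empagliflozin users as a whole resemble DPP-4 inhibitor users. It does not make 10 mg users resemble 25 mg users, or either dose group resemble the never-exposed reference. A covariate can be well balanced between drugs and badly unbalanced between doses. The better the matching works, the more surely that covariate leaves the model used for the dose contrasts.

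eGFR is the clearest case, because the protocol makes it a condition for the higher dose. The other condition, need for tighter control, is partly covered because HbA1c is a candidate covariate. Nothing comparable covers eGFR.

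The dose-related hazard ratios are a stated secondary objective, and both documents promise adjusted estimates. The protocol also cites a dose pattern from an earlier trial: "three (0.1%) and nine (0.4%) cases of bladder cancer were observed in persons exposed to 10 mg and 25 mg empagliflozin, respectively". The same sentence reports five cases (0.2%) on placebo, and that section concludes that the trials showed no increased risk. The pattern is a reason to estimate the dose contrast cleanly. It is not evidence of a dose effect.

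**Working it through.** The documents give no power, event count or effect size for the dose analyses, so there is no planned figure to reproduce. They also give no distribution of eGFR or age by dose. The check therefore asks whether the rule can omit a covariate that separates the doses, and how large the resulting bias could be on stated assumptions.

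**1. Can eGFR pass the screen and still separate the doses?** Assume low eGFR in 5% of 25 mg users and 15% of 10 mg users, with 20% of empagliflozin users on 25 mg. Overall prevalence is 0.8 × 0.15 + 0.2 × 0.05 = 0.13. If matched DPP-4 users also have 0.13, the between-drug standardised difference is 0% and eGFR is left out. With the SAP 6.6.2 formula, the between-dose difference is 0.10 / √[(0.05 × 0.95 + 0.15 × 0.85)/2] = 0.10/0.296 = 33.8%.

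**2. Bias from omitting it.** The factor for 25 mg versus 10 mg is [1 + p25(RR − 1)] / [1 + p10(RR − 1)], where p is the prevalence of low eGFR and RR is the assumed rate ratio for the low-eGFR (and older) group. The table uses p25 = 5% and a true hazard ratio of 1.50.

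| p10 | Between-dose difference | RR 1.3 | RR 1.5 | RR 2.0 |
|---|---|---|---|---|
| 15% | 33.8% | 0.971 → 1.46 | 0.953 → 1.43 | 0.913 → 1.37 |
| 25% | 58.3% | 0.944 → 1.42 | 0.911 → 1.37 | 0.840 → 1.26 |
| 35% | 80.9% | 0.919 → 1.38 | 0.872 → 1.31 | 0.778 → 1.17 |

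**3. eGFR and age together.** Assume 35% of patients are older; low eGFR in 40% of older and 10% of younger patients; 25 mg used by 8% of those with low eGFR and 35% of the rest; relative rates 2.0 (older) and 0.8 (younger), multiplied by 1.3 for low eGFR.

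- Cell shares: older/low 0.14, older/normal 0.21, younger/low 0.065, younger/normal 0.585. Relative rates: 2.6, 2.0, 1.04, 0.8.
- Cell weights at 25 mg are 0.0112, 0.0735, 0.0052 and 0.20475 (sum 0.29465). Mean rate before any drug effect = 0.3453/0.29465 = 1.172.
- Cell weights at 10 mg are 0.1288, 0.1365, 0.0598 and 0.38025 (sum 0.70535). Mean rate = 0.9743/0.70535 = 1.381.
- Bias factor = 1.172/1.381 = 0.849, so a true 1.50 reads 1.27.

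The between-dose differences are then about 60% for eGFR and 19% for age. A simulated matched cohort of 20 million with these inputs showed between-drug differences of about 0.1%. It gave a hazard ratio of 1.27 with both covariates omitted and 1.50 with both entered.

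**4. Does another planned analysis cover this?** In Table 16 the hazard ratios stratified by age, sex and propensity-score quartile, and the marginal structural model, all use the as-treated exposure. None uses dose or duration. No visible table reports balance by dose level.

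**The case against.** Several points on the other side stand.

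- **The model is not confined to covariates unbalanced between drugs.** A reader might infer that from the base-model rule. The dose analyses use the adjusted model, which also considers nine time-dependent variables. These include HbA1c, and also stones and urinary infection, which correspond to risk factors named in Protocol 6.1. The gap concerns baseline covariates only.
- **Only eGFR is linked to dose by the documents.** A reader might take it as established that age separates the doses. No passage says so for age, sex or smoking. Age is an inference through eGFR, because the SAP's CKD-Epi formula contains an age term. Conversely, Protocol 6.1 names smoking and sex as risk factors, and Table 1 shows higher rates over age 40 (82.8 versus 43.0 per 100,000 person-years in the Nordic countries), but the list in 6.1 does not name eGFR. No single covariate is documented both to differ by dose and to raise risk.
- **Dose is time-dependent.** With a 10 mg starting dose, one patient can contribute time at 10 mg and later at 25 mg. The illustrations use two fixed groups.
- **Part of the SAP is not public.** The visible text goes from 6.7.3.2 to 6.10, and further specification of these models could lie between. The point rests on 6.7.2 and Table 16.
- **Forcing terms in is not free.** UK renal cancer would give about 26.5/100,000 × 16,360 × 2.4 = 10 empagliflozin events, and about 42 in all at 1:3 with no effect. Age has seven categories and eGFR six, while SAP 6.7.2 requires at least five events per category.

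These points limit the size and certainty of the concern. They do not make between-drug balance a valid screen for between-dose confounding.

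**Conclusion.** The point holds as a gap in the secondary analyses. As written, the plan can leave out baseline eGFR, and any imbalance in age, sex or smoking, from every dose and duration model. This may bias the dose contrasts.

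For 25 mg versus 10 mg the likely direction is towards masking a gradient, if lower eGFR or older age raises risk. The size is unknown. The bias factors of 0.97 to 0.78 show what assumed inputs produce and are not estimates for this study.

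A reader might go further and infer that the study will report a flat or inverse gradient, or that the top cumulative-dose quartile carries the same bias. The documents support neither. Cumulative dose and duration also depend on persistence and follow-up, so the direction there is uncertain.

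The three primary objectives are unaffected, because the as-treated comparison is the contrast that the matching and the balance screen were built for. This is a should-fix for a secondary objective, not a must-fix.

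**What to change.** For the three secondary exposure definitions only, amend SAP 6.7.2 and Table 16 as follows.

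1. Enter baseline age and sex in the Cox model whatever their between-drug standardised difference. Add baseline eGFR and smoking wherever the missing-data rule in SAP section 9 leaves them usable. Keep HbA1c as already listed.
2. Where events are few, use age and eGFR as continuous or collapsed terms, so that the five-events-per-category rule does not exclude them.
3. Exempt these terms from the convergence-removal ranking. It removes the smallest between-drug difference first, so well-matched forced terms would be the first to go.
4. Report baseline characteristics for 10 mg, 25 mg and matched DPP-4 inhibitor users in each country, stating the time point at which dose is classified.
5. Align Protocol Table 4, footnote 4, so that the two documents agree.

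The cost is wording in both documents, one more descriptive table per country and a few degrees of freedom on data already collected. It will be felt mainly for renal cancer. eGFR will be limited in Finland: it comes from regional medical records with about 26.7% coverage (Protocol 8.9.2). If coverage translates directly, about 73% of patients would lack a value, which exceeds the 50% level at which SAP section 9 considers removal. Age and sex remain available there, and the report should say which country models include eGFR.
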